7.7.5.2. Analyses of Other Secondary Endpoints in the RW Period

The following endpoints will be analyzed using the same method for the major secondary endpoints:

- Proportion of subjects who maintained Clinical Response at Week 8 and Week 24 of the RW period
- Percentage of days with no or minimal pain (pain ≤ 2 on the 11 point NRS) in the first 8 weeks and 24 weeks of the RW period

- Proportion of subjects with absent or minimal pericarditis symptoms (based on the 7-point rating scale of PGIPS) at Week 8 and Week 24 of the RW period

The following endpoints will be analyzed using the same method for the primary endpoint:

- Time to pericarditis pain NRS ≥ 4
- Time to CRP level ≥ 1 mg/dL. This is for elevation of CRP for which no other cause other than pericarditis was identified.
- Time to pericardial rub
- Time to widespread ST segment elevation or PR segment depression on ECG
- Time to new or worsening pericardial effusion on ECHO

A mixed model with repeated measures (MMRM) will be used in the analysis of the endpoints below. In the model, subjects will have repeated measures for the response variable change from baseline of the endpoint. For endpoints without repeated measures with subjects, e.g., health-related quality-of-life assessment, the analysis of covariance will be applied. The explanatory variables will include the baseline value, treatment arm, and the variables for stratification at randomization. The p-value for treatment comparison will be calculated at each scheduled assessment for at least 24 weeks as part of the summary statistics. This is done with the understanding that the comparison could be biased due to dropouts or subjects with pericarditis recurrence.

- Change over time in CRP levels
- Change over time in the subject's assessments of pericarditis pain (weekly average)

The CMH test will be used in the analysis of the endpoints below, stratified by the stratification variables for randomization.

- Proportion of patients without pericarditis recurrence in the first 24 weeks of the RW period
- Number (percent) of subjects with absent or minimal pericarditis activity based on the PGA-PA

The following endpoints will be summarized without formal hypothesis testing:

- Change in the SF 36 Physical and Mental Component Scores and domain scores
- Change in the EQ 5D 5L: Health score and Index value, respectively
- Change in the subject's sleep quality: sum of the ISI scores.

The following exploratory endpoint in the MRI sub-study will be summarized by treatment

■

■

■

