6.1.4. Pericarditis Recurrence Assessment: Clinic Visit

If a subject experiences symptoms consistent with pericarditis recurrence, he/she should contact the study Investigator immediately for evaluation (including in the LTE). It is possible that a subject may have assessments performed remotely, however, assessments are also expected to be performed at the study site as soon as possible. Required assessments include:

- Evaluate pericarditis pain on the 11-point NRS.
- Evaluate concomitant medications as well as pericarditis concomitant medications.
- Obtain laboratory samples for CRP (local and central) (the POC device provided by Kiniksa Pharmaceuticals is the preferred method for local laboratory CRP assessment).
- Acquire a 12 lead ECG.
- Acquire a cardiac ECHO per core laboratory imaging parameters; this ECHO is read locally for the purpose of pericarditis recurrence assessment and is then submitted to the ECHO core laboratory for central review.
- Perform an abbreviated physical examination, height and body weight.
- For subjects >18 years, complete the SF-36, EQ-5D-5L, ISI.
- For all subjects, complete the PGIPS score.
- The Investigator is to complete the PGA PA.
- Obtain central laboratory samples for PK, ADAs, and biomarkers.
- Other procedures deemed necessary per the Investigator or delegated site personnel (e.g. MRI for sub-study subjects).

Upon having completed the evaluation, if the Investigator makes a clinical diagnosis that the subject is having a pericarditis recurrence event, he/she should contact the [REDACTED] medical monitor to review and confirm that all assessments have been performed and collected. Upon [REDACTED] medical monitor confirmation of completion of the assessment, the Investigator commences as described in Section 6.2.3.

Subjects treated for a pericarditis recurrence event will continue to follow the same visit schedule described for the RW period (Section 6.1.5).

Source documentation including the assessments and evaluations used to confirm a pericarditis recurrence event, are required to be sent to CEC.

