7.2.2. Other Secondary Endpoints

All time-to-event endpoints start from the day of randomization. The following variables will be analyzed:

- Proportion of subjects who maintained Clinical Response at Week 8 and Week 24 of the RW period, respectively
- Percentage of days with no or minimal pain (pain ≤ 2 on the 11-point NRS) in the first 8 weeks and 24 weeks of the RW period, respectively
- Proportions of subjects with absent or minimal pericarditis symptoms (based on the 7 point rating scale of PGIPS) at Week 8 and Week 24 of the RW period, respectively
- Proportion of subjects without pericarditis recurrence in the first 24 weeks of the RW period
- Time to pericarditis pain NRS ≥ 4
- Time to CRP level ≥ 1 mg/dL. This is for elevation of CRP for which no other cause other than pericarditis was identified.
- Time to pericardial rub
- Time to widespread ST-segment elevation or PR-segment depression on ECG, whichever occurs first
- Time to new or worsening pericardial effusion on ECHO
- Change in category of ECHO pericardial effusion size at week 24 and end of RW based on central labs
- Change over time in CRP levels
- Change over time in the subject's assessments of pericarditis pain (weekly average)
- Proportion of subjects with absent or minimal pericarditis activity based on the PGA-PA over time

- Proportion of subjects with absent or minimal pericarditis activity over time based on the PGIPS over time
- Change over time in SF-36 Physical and Mental Component Scores and domain scores (Physical Functioning, Role-Physical, Bodily Pain, General Health, Vitality, Social Functioning, Role-Emotional, and Mental Health domains)
- Changes in SF-6D, 6 domain scores and utility index
- Change in EQ-5D-5L. There are 6 questions in this instrument (Section 6.2.1.8). Each of the first 5 questions has 5 levels, from level 1 (best) to level 5 (worst). They are mobility, self-care, usual activities, pain/discomfort, and anxiety/depression. The sixth question is the health on the day, from 0 (the worst) to 100 (the best) (van Reenen and Janssen 2015). The levels of the first 5 questions (EQ-5D-5L profile) will be converted to an index value. Change from baseline in each one of these 7 values will be an endpoint.
- Change in subject's sleep quality assessed with the ISI (Section 6.2.1.9). There are 7 items in the ISI. Change in ISI total score, which is the sum of the 7 items over time, will be the endpoint.

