7.7.4. Analysis of Primary Efficacy Endpoint

Primary analysis of this study will be triggered after at least the 22nd CEC-confirmed pericarditis recurrence events have been accrued. The log rank test will be the primary method for the analysis of time to recurrence, stratified by the stratification variables for randomization. Detailed censoring rules will be described in the SAP.

A sensitivity analysis will be performed based on the Investigator's judgement of pericarditis recurrence. Additional sensitivity analyses may be defined in the SAP.

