- m All procedures are to be completed prior to study drug administration.
- n The first dose of study drug is a loading dose. Adult subjects receive 2 SC doses 160 mg (total 320 mg); pediatric subjects (subjects ≥ 12 and < 18 years of age) receive 2 SC doses of 2 x 2.2 mg/kg.
- o Study drug administration is once weekly with a minimum of 5 days required between doses.
- p Randomization and subsequent study drug dispensing to occur after confirmation of Clinical Response (see definition of Clinical Response in Section 6.2.2).
- q The Randomization visit serves as both the RI Week 12 visit and the RW baseline visit.
- s PK and ADA samples will be collected prior to study drug administration. PK at enrollment/baseline will be taken from ADA

Table 3: Study Schedule of Activities – Randomized Withdrawal

Trial Period	RANDOMIZED WITHDRAWAL (event-driven) ^m								END OF RANDOMIZED WITHDRAWAL (EORW) ^t
Visit Name	RW Week 4	RW Week 8	RW Week 12	RW Week 16	RW Week 20	RW Week 24	RW Every 8 Weeks	RW Every 8 Weeks	Per Announced End Date ^u /LTE-Baseline
Visit Window ^b (days)	+/- 2	+/- 2	+/- 2	+/- 2	+/- 2	+/- 2	+/- 2	+/- 2	+/- 7
Visit Type	TC/RN	Clinic	TC/RN	Clinic	TC/RN	Clinic	TC/RN	Clinic	Clinic
Informed Consent Form									X
Concomitant medications	X	X	X	X	X	X	X	X	X
Pericarditis Concomitant medications	X	X	X	X	X	X	X	X	X
Full Physical Examination ^e						X			X
Abbreviated Physical Examination ^d									
Body weight and height		X		X		X		X	X
12-Lead ECG						X			X
Echo ^e						X ^e			X ^e
MRI (substudy only)						X			
Pericardial pain (11-point NRS)	DAILY								
EQ-5D						X			X
SF-36						X			X
ISI						X			X
PGIPS		X		X		X		X	X
PGA-PA		X		X		X		X	X
Hematology, Chemistry Labs (Central)		X				X		X	X
Lipid Panel (Central) ^h						X			X
CRP (Local)									

Trial Period	RANDOMIZED WITHDRAWAL (event-driven) ^m								END OF RANDOMIZED WITHDRAWAL (EORW) ^t
	RW Week 4	RW Week 8	RW Week 12	RW Week 16	RW Week 20	RW Week 24	RW Every 8 Weeks	RW Every 8 Weeks	Per Announced End Date ^u / LTE-Baseline
Visit Window ^b (days)	+/- 2	+/- 2	+/- 2	+/- 2	+/- 2	+/- 2	+/- 2	+/- 2	+/- 7
Visit Type	TC/RN	Clinic	TC/RN	Clinic	TC/RN	Clinic	TC/RN	Clinic	Clinic
CRP(Central)	X	X	X	X	X	X	X	X	X
PK (Central) ^s		X				X			X
ADA (Central) ^s						X			X
Biomarkers (Central)		X				X			
Urine Pregnancy ^j (Local or Central)									X
Urinalysis									X
IWRS Subject Status Update									X
IWRS Weight Input (pediatric only)		X		X		X		X	X
IWRS Drug Dispensing		X		X		X		X	X ^v

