In Clinic Study Drug Administration ^o		X		X		X		X	X ^v
Outpatient Study Drug Administration ^o	X	WEEKLY							
Study Drug Compliance Review	X	X	X	X	X	X	X	X	X
Assessment of Pericarditis Recurrence	X	X	X	X	X	X	X	X	X
Adverse Event Reporting ^l	X	X	X	X	X	X	X	X	X

b Scheduling of visits within visit windows requires cautious planning to ensure there is no interruption to subject evaluation and study drug treatment.

c Full physical examination includes at minimum evaluation of vital signs, head, eye, ear, nose, and throat as well as cardiovascular, dermatological, musculoskeletal, respiratory, GI, genitourinary, and neurological systems. The decision to perform examination of genitourinary system should be guided by clinical judgement.

d Abbreviated physical examination includes at minimum evaluation of vital signs, lung and heart sounds, including evaluation for pericardial rub.

e ECHO is required to be obtained according to the central core lab parameters and then read locally and submitted to the central core lab for separate review and analysis.

h Lipid panels are non-fasting and are to be drawn at a minimum of every 6months during the randomization withdrawal and LTE periods, or more frequently as needed, with mandated evaluations as detailed in the schedule of events.

- j For women of child bearing potential - urine pregnancy testing can be repeated as needed throughout the course of the study and serum pregnancy can be drawn as needed; urine pregnancy is required to be performed at enrollment and 6 weeks after the last dose of study drug.
- l Adverse event reporting begins following the subject providing informed consent.
- m All procedures are to be completed prior to study drug administration.
- o Study drug administration is once weekly with a minimum of 5 days required between doses.
- s PK and ADA samples will be collected prior to study drug administration. PK at enrollment/baseline will be taken from ADA. As required, ADA samples will be collected at EOS, ET, and Unscheduled visits.
- t The EORW visit serves as both the last visit of the RW period and the baseline visit of the LTE period.
- u For all subjects, the final clinic visit of the end of RW period is to be scheduled once the End of the Randomization Withdrawal end date is announced by Sponsor. This includes subjects that are taking blinded study drug, open-label rilonacept, or who have prematurely discontinued study drug.

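### Time to rub, ECG change and effusion are log-rank tested although, before Week 24 of the RW period, these signs are sought mainly at suspected-recurrence visits, so the p-values partly restate the primary endpoint

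*Protocol*

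**What the plan says.** Section 7.2.2 lists the three sign endpoints among the other secondary endpoints (for example "Time to new or worsening pericardial effusion on ECHO") and starts the clock at randomization: "All time-to-event endpoints start from the day of randomization". Section 7.7.5.2 then says "The following endpoints will be analyzed using the same method for the primary endpoint" and lists five endpoints: pain, CRP, rub, ECG change and effusion. The primary method is in Section 7.7.4: "The log rank test will be the primary method for the analysis of time to recurrence, stratified by the stratification variables for randomization".

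The examinations behind these endpoints are set out in Section 13.1:

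- **Table 3 (RW period).** 12-lead ECG, ECHO and full physical examination are marked at Week 24 and EORW only. The row "Abbreviated Physical Examination ^d" has no visit marked, although Weeks 8 and 16 are clinic visits. Its footnote is where rub is named: "Abbreviated physical examination includes at minimum evaluation of vital signs, lung and heart sounds, including evaluation for pericardial rub". The full examination covers the cardiovascular system without naming rub.
- **Table 5 and Section 6.1.4 (suspected recurrence).** All three assessments are required when symptoms bring the subject in: "Acquire a 12 lead ECG", an ECHO to core-laboratory parameters, and "Perform an abbreviated physical examination, height and body weight".

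Pain and CRP, the other two endpoints in the same list, are collected on a common schedule in both arms: pain daily and central CRP at every RW visit.

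**The concern.** A log-rank test treats every subject without a recorded event as observed and event-free. For these signs, a subject without symptoms is normally not examined until Week 24 or EORW, while a subject with a suspected recurrence is examined at once. The timing of examination thus depends on the primary event, and the trial expects that event to come much sooner on placebo. An arm difference in time to first detected sign can arise because one arm was looked at earlier and more often, even if the sign is no more common there.

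The stake is interpretation. Three small p-values for rub, ECG and effusion could pass for objective support separate from the primary result, when part of what they show is that result again.

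**Working it through.** **1. The plan's own figure.** Section 7.4 gives one-sided alpha 2.5%, power 90%, hazard ratio 0.244 and 1:1 allocation. Schoenfeld's formula gives 4 × (1.960 + 1.282)² / (ln 0.244)² = 42.03 / 1.990 = 21.1, rounded up to 22 events (power 0.911 at 22). The stated 22 reproduces and is not in dispute.

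**2. How unequal the examination is.** Section 7.4 assumes exponential recurrence with a placebo median of 8 weeks, so the placebo hazard is ln 2 / 8 = 0.0866 per week and the rilonacept hazard is 0.244 × 0.0866 = 0.0211. The probability of a recurrence, and so of a recurrence visit, by week t is 1 − exp(−hazard × t):

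| By week | Placebo | Rilonacept |
|---|---|---|
| 8 | 50.0% | 15.6% |
| 16 | 75.0% | 28.7% |
| 24 | 87.5% | 39.8% |

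If everyone is followed to Week 24, the mean time to first look (the earlier of recurrence and Week 24) is (1 − exp(−24 × hazard)) / hazard. That is 0.875 / 0.0866 = 10.1 weeks on placebo and 0.398 / 0.0211 = 18.8 weeks on rilonacept, a gap of 8.7 weeks.

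**3. Does unequal looking alone move the test?** Simulation with 25 per arm, all followed to Week 24, one-sided 0.025, unstratified log-rank. A transient sign is present at any look with the same probability in both arms. With looks at recurrence and Week 24, rejection is 10.3%, 16.2% and 23.6% at assumed prevalence 20%, 30% and 40%. With looks at Weeks 8, 16 and 24 in both arms, it is 2.3% to 2.8% over assumed prevalence 5% to 40%. The examination schedule is therefore the cause.

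**4. The same check under the Version 3.0 stopping rule.** Step 3 is not quite this trial. Follow-up of all 50 to Week 24 implies 25 × 0.875 + 25 × 0.398 = about 32 recurrences, whereas Sections 3.1.3 and 7.7.4 end the RW period once 22 confirmed events have accrued. There is no 24-week minimum, and Section 6.1.6 gives every subject an EORW visit. Stopping at the 22nd recurrence with an EORW look for all, and spreading randomization over an assumed 0 to 52 weeks, gives these one-sided rejection rates at nominal 2.5%:

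| Sign unrelated to arm | Assumed prevalence | Rejection |
|---|---|---|
| Transient | 20% | about 6% to 10% |
| Transient | 30% | about 11% to 14% |
| Transient | 40% | about 14% to 18% |
| Fixed trait of the subject | 10% to 40% | about 2% to 7% |

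For a persistent sign with gradual onset (assumed 10% to 50% by Week 24), the version of step 3 with follow-up to Week 24 gives 2.3% to 3.2%. This is close to nominal, because the later scheduled look finds the sign in both arms.

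The protocol gives no sign frequencies, so every prevalence here is an assumption.

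**The case against.** **The null is artificial.** Rub, ST/PR change and new effusion are diagnostic criteria for an acute episode (Section 1), and recurrence is defined as pain with objective support (Section 6.2.3). A drug with a recurrence hazard ratio of 0.244 and no effect on these signs is hardly coherent. This stands as a limit on size: real recurrences bring real signs, so the p-values are partly, not wholly, a product of who was examined. A reader might infer that they carry no information about the drug. The documents do not support that.

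**There are other early looks.** An end-of-treatment visit includes ECG, ECHO and full examination, EORW may fall before Week 24, unscheduled visits are allowed, and symptom-directed examination is possible at any site visit. This is true, but apart from EORW these looks also follow the subject's course, so they do not give the arms a common schedule.

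**Little rests on these tests.** They lie outside the gatekeeping and Hochberg procedure of Section 7.7.3, and the protocol nowhere calls them independent evidence. This stands and limits the weight of the point.

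**The obvious replacements have their own faults.** Comparing sign prevalence at Week 24 or EORW by arm is contaminated, because subjects who meet the bailout criteria switch to open-label rilonacept whatever their arm. Comparing signs among recurrences conditions on a post-randomization event, with the 22 events expected to split about 16 to 6. This also stands and narrows the fix.

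**The SAP might deal with it.** Censoring rules belong there, but no rule can supply an ECG, ECHO or rub examination that was not scheduled. The caution about bias in Section 7.7.5.2 is attached to the repeated-measures comparisons and concerns dropout and recurrence. It does not mention examination timing.

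**Conclusion.** The point holds in moderate form. For rub, ECG change and effusion, the protocol pairs a log-rank test from randomization with an examination schedule that, before Week 24, is driven mainly by suspected recurrence. For a transient sign unrelated to arm, false significance would occur in roughly 6% to 18% of trials instead of 2.5%. Inflation is small for a fixed trait and near none for a persistent sign of gradual onset.

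These sizes rest on the recurrence assumptions in Section 7.4, a stop at 22 events with an EORW look for all, assumed prevalence of 20% to 40% for the transient case, accrual over 0 to 52 weeks, and an unstratified test.

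A reader might take the 23.6% in step 3 as the error rate of this trial. It is not, because it assumes follow-up of everyone to Week 24, which Version 3.0 does not require. Nor does the point reach the primary endpoint, which is time to recurrence itself, or the major secondary endpoints. It should be corrected because the change is cheap, but it is not a threat to the trial's main claim.

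**What to change.** In Section 7.7.5.2, move the three sign endpoints out of the log-rank list and into the group the section already sets aside for summary with no hypothesis test. Keep descriptive time-to-event summaries by randomized arm, and state that ascertainment before Week 24 is driven by suspected recurrence. Align Section 7.2.2 accordingly.

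Signs found at recurrence may be listed by arm, descriptively only. Any Week 24 or EORW summary of the signs should be split by whether the subject had already switched to bailout rilonacept, and should carry a note that it is not a randomized comparison.

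Optionally, mark the existing blank abbreviated-examination row in Table 3 at the RW Week 8 and Week 16 clinic visits, so that rub is sought on a common schedule. This would not help the ECG or ECHO endpoints.

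Cost: the main change is wording only and needs no new data; three supportive p-values are lost. The optional rub check adds a few minutes at visits that already take place.

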5. STUDY TREATMENTS

5.1. Method of Assigning Subjects to Treatment Groups

In the single-blind RI period, all subjects will receive blinded rilonacept at the same dose through Week 12; subjects will be blinded to the time of transitioning to RW. Subjects who stopped background SOC pericarditis therapy and who achieve Clinical Response on rilonacept at RI Week 12/RW baseline will be randomly assigned in a double-blind manner to continue to receive blinded rilonacept or matching placebo using a 1:1 allocation ratio. The definition of Clinical Response is provided in Section 6.2.2. An interactive web response system (IWRS) will be used to administer the randomization schedule. Biostatistics will generate the randomization schedule using SAS[®] software Version 9.4 or later (SAS Institute Inc, Cary, North Carolina) for the IWRS, which will link sequential subject randomization numbers to treatment codes. The randomization schedule will be stratified by 2 factors:

- Oral CS use at baseline (RI baseline, i.e., beginning of RI period): yes or no
- Diagnosis of recurrent idiopathic pericarditis (RI baseline): yes or no

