7.4. Sample Size Calculations

For the purpose of sample size estimation, time to pericarditis recurrence is assumed to follow an exponential distribution. An event of interest is defined as a subject's first adjudicated recurrence of pericarditis. The following assumptions are used in the sample size calculation using EAST 6.4.1:

- 1-sided significance level 2.5%
- Power 90%
- Median time to event (in weeks) in placebo 8
- Hazard ratio (rilonacept/placebo) 0.244
- Percentage of subjects in the RI period that will not reach RW 10%

Given these assumptions, a total of 22 adjudicated pericarditis recurrence events is required to achieve the power. About 25 subjects per arm (a total of 50 subjects) will be randomized. Considering 10% of subjects in the RI period that will not reach the RW period, approximately 56 subjects will be enrolled in this study.

Patient enrollment and the pericarditis recurrence event accrual will be closely monitored during the study. The monitoring activities will be done in a blinded fashion during the RW period. If the number of patients randomized is less than 50 and/or the time anticipated for the number of events required for the analysis of primary efficacy endpoint significantly exceeds the projected timeline, additional patients may be enrolled and/or randomized at Kiniksa Pharmaceutical's discretion. However, at this time it is anticipated that no more than 100 subjects will be enrolled into this study.

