7.5. Analysis Sets

The following analysis sets will be used in the statistical analyses.

Intent-to-Treat (ITT) Analysis Set: All subjects who are randomized in the RW period will be included in the ITT analysis set. The primary analysis for efficacy endpoints in the RW period will be based on the ITT analysis set. Treatment comparisons for all ITT analyses will be based on each subject's treatment assignment from randomization.

ITT Week 24 analysis set: All subjects randomized at least 24 weeks before data cutoff will be included. This analysis set will be used for secondary efficacy endpoints measured at week 24 in the RW period.

ITT Week 16 analysis set: All subjects randomized at least 16 weeks before data cutoff will be included. This analysis set will be used for secondary efficacy endpoints measured at week 16 in the RW period.

ITT Week 8 analysis set: All subjects randomized at least 8 weeks before data cutoff will be included. This analysis set will be used for secondary efficacy endpoints measured at week 8 in the RW period.

Safety Analysis Set: All subjects who received at least 1 dose of study drug in the RI period will be included in the safety analysis set (SS). Safety analyses will be based on the actual treatment a subject received.

Run-in Analysis Set: All subjects who received at least 1 dose of study drug in the RI period will be included in the RI analysis set (RIS).

Run-in Week 12 Analysis Set: All subjects who received the first dose in the RI period at least 12 weeks before data cutoff. This analysis set will be used for secondary efficacy endpoints measured at Week 12 in the RI period.

Long Term Extension Analysis Set: All subjects who received at least 1 dose of study drug in the long-term extension period will be included in the long-term extension analysis set

Per-protocol Analysis Set: The per protocol (PP) analysis set is a subset of the ITT analysis set with the exclusion of subjects with major protocol violations or violations that may potentially bias statistical analyses or the ethical conduct of the study. The criteria of these violations will be determined prior to unblinding. This analysis set may be used for sensitivity analyses for efficacy endpoints in the RW period.

Pharmacokinetic Analysis Set: The PK analysis set includes subjects who receive at least 1 dose of study drug and have at least 1 PK sample. The PK analysis set will be used for all PK analyses.

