7.7.1. General Methods

Statistical analysis will be performed using SAS[®] software Version 9.4 or later. Continuous variables will be summarized using the mean, the standard deviation, median, minimum value, and maximum value. Time-to-event variables will be summarized using percent censored, event rate, and 25th, 50th, and 75th percentiles with 95% CI, if estimable.

Categorical variables will be summarized using frequency counts and percentages. Data will be listed in data listings.

At each of RI and RW periods and in the LTE, baseline will be the last value before the first dose of study drug within each individual period unless otherwise specified. For change-over-time endpoints in the RW period, by-visit analysis will be performed at each scheduled visit for at least 24 weeks.

The analysis for treatment comparison will be triggered after at least the 22nd CEC-confirmed pericarditis recurrence events have been accrued. At that time, randomization will be closed, and subjects will return to study sites for the EORW visit. At that point study treatment will stop (completing the database for the primary efficacy endpoint analysis), and subjects will either continue into the LTE or complete their study participation. Missing data due to end of RW period will be considered as missing at random. Handling of missing values will be described in the SAP.

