7.7.3. Testing Hypotheses and Multiplicity Adjustment

All statistical tests for the treatment comparison of efficacy endpoints in the RW period will be based on the ITT analysis set with 1-sided $\alpha=0.025$ unless otherwise specified. For each endpoint, the null hypothesis is that the effects of rilonacept and placebo are the same. The alternative hypothesis is that rilonacept is better than the placebo.

In order to control the overall 1-sided type I error rate at the 0.025 level, a gatekeeping procedure in combination with Hochberg's procedure will be applied to testing the primary and major secondary endpoints. If the 1-sided p-value for testing the primary endpoint is ≤ 0.025 , a significant treatment effect on the primary endpoint will be claimed.

Section 7.2.1 provides the order of major secondary endpoints. If the primary endpoint is significant, the first major secondary endpoint, i.e., proportion of subjects who maintained Clinical Response at Week 24 of RW period will be tested at 1-sided $\alpha=0.025$. A significant treatment effect on this major secondary endpoint will be claimed if the 1-sided p-value is ≤ 0.025 . If the treatment effect is not significant on the primary endpoint, significance on this major secondary endpoint cannot be claimed regardless of the result.

If both primary and first major secondary endpoints are significant following the above procedure, the second and third major secondary endpoints defined in Section 7.2.1 will be tested with Hochberg's procedure at overall 1-sided $\alpha=0.025$. If both 1-sided unadjusted

p-values are ≤ 0.025 , claim significance of rilonacept for both endpoints. If the larger 1-sided p-value is > 0.025 , compare the smaller 1-sided p-value with 0.0125. If the smaller 1-sided p-value is ≤ 0.0125 , claim significance of rilonacept on this endpoint.

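### The 24-week recurrence-free proportion keeps its CMH test although RW can now close before Week 24; a censored-data analysis would use every randomized subject

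*Protocol*

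**What the plan says.** Section 7.7.5.2 of Version 3.0 lists the "Proportion of patients without pericarditis recurrence in the first 24 weeks" of RW among the endpoints tested by CMH, stratified by the randomization factors. It names no analysis set for this endpoint.

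Three other sections bear on it:

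- **Section 7.5** defines an ITT Week 24 set: "All subjects randomized at least 24 weeks before data cutoff will be included". The set is for secondary endpoints measured at week 24.
- **Section 7.7.3** says tests in RW are "based on the ITT analysis set", unless otherwise specified.
- **Section 7.7.1** closes randomization and brings subjects in for the EORW visit once at least 22 confirmed events have accrued. It adds: "Missing data due to end of RW period will be considered as missing at random". Handling of missing values is left to the SAP.

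Version 2.0 used the same CMH test for the same endpoint, but its Section 7.7.4 also required all subjects in RW to have been treated for 24 weeks. The summary of changes in Section 13.3 of Version 3.0 records that this requirement was dropped.

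**The concern.** The endpoint is time to recurrence cut at 24 weeks. Under Version 2.0 the 24-week status of nearly everyone would have been known by the analysis, so a yes/no test was workable. Under Version 3.0 many subjects will be administratively closed out before Week 24 with their status unknown, and the test was not changed to match.

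Restricting the analysis to the ITT Week 24 set solves this by discarding recent subjects, including those whose recurrence was observed. The result may be a very small comparison of the outcome closest to the primary endpoint, when follow-up already collected on every randomized subject could be used.

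**Working it through.** **1. Inputs, all from Protocol Version 3.0.** Section 7.4: "1-sided significance level 2.5"%, power 90%, "Median time to event (in weeks) in placebo 8", "Hazard ratio (rilonacept/placebo) 0.244", exponential times, 22 events, about 50 randomized, 10% run-in loss. Section 5.1: "matching placebo using a 1:1 allocation ratio".

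**2. The plan's own figures.** Schoenfeld: d = (1.960 + 1.282)² / (0.25 × (ln 0.244)²) = 21.1, so 22 events, as stated. Enrolment: 50 / 0.9 = 55.6, so 56, as stated.

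**3. True Week 24 values under the plan.**

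- Placebo: hazard ln 2 / 8 = 0.0866 per week; recurrence-free exp(−0.0866 × 24) = 12.5%.
- Rilonacept: hazard 0.244 × 0.0866 = 0.0211 per week; recurrence-free 0.125^0.244 = 60.2%.

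**4. Assumptions.** The protocol gives no randomization rate. I took 50 subjects entering uniformly over 26 to 104 weeks (50/26 = 1.9 down to 50/104 = 0.5 per week), cutoff exactly at the 22nd event, and four strata with assumed shares 0.42/0.42/0.08/0.08. Each scenario was simulated at least 3,000 times. Repeat runs agree to within about three percentage points.

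**5. Likely reading: ITT Week 24 set.** Shares are of subjects randomized by the cutoff.

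| Accrual of 50 (weeks) | Under 24 weeks at cutoff | Stratified CMH power, Week 24 set | Stratified log-rank power, truncated at Week 24, all ITT |
|---|---|---|---|
| 26 | 89% | 10% | 83% |
| 40 | 70% | 37% | 82% |
| 52 | 59% | 44% | 80% |
| 68 | 50% | 50% | 77% |
| 104 | 37% | 58% | 75% |

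At 52 weeks, for example, about 40.8 subjects have been randomized by the cutoff and 16.9 are in the set: 1 − 16.9/40.8 = 59%. About 10 of the 22 events fall outside the set. Across the table the set holds about 5 to 21 subjects. At a steady rate, the loss passes one half at about 0.75 to 0.8 randomized per week. The last column should not be set against the plan's 90%, which is a formula value for an untruncated test.

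**6. Other reading: full ITT, closed-out subjects counted as recurrence-free.** Apparent proportions would be about 22% to 35% on placebo (true 12.5%) and 66% to 75% on rilonacept (true 60.2%).

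**7. Does the alternative behave?** At steady rates of 0.4 to 1.5 per week the mean Kaplan-Meier estimates at Week 24 are 12.5% to 13.0% and 59% to 60%, close to truth. At 3 to 4 per week almost nobody reaches Week 24 and they drift to 19% to 24% and 65% to 69%. The truncated log-rank test has one-sided type I error of 2.4% to 2.9% at 52-week accrual.

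**The case against.** The strongest reply is that the Week 24 set is a legitimate choice. Membership depends on randomization date, not on arm or outcome, so the comparison stays randomized. Dropping recent subjects who recurred is necessary if recent event-free subjects are dropped too, since keeping only the former would bias the proportion. This stands: the set is inefficient, not biased.

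A reader might infer that the plan counts a subject closed out at Week 5 as free of recurrence for 24 weeks. The documents do not support that. Section 7.7.3 yields where another set is specified, Section 7.5 probably specifies one, and Section 7.7.1 treats what follows closure as missing. The opening is only that the endpoint covers the first 24 weeks while Section 7.5 speaks of endpoints measured at week 24. The SAP could also impute under missing at random and then apply CMH, so the two readings are not the only ones.

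A reader might also take a loss of half or more as a fact. It depends on an unstated accrual rate, and a cutoff later than the 22nd event would reduce it. Section 3.1.4 projects about 36 weeks of minimum dosing, which would fit 12 weeks of run-in plus 24 of RW, but it is a projection and sets no minimum.

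Finally, the truncated log-rank test overlaps the primary test and compares hazards over 0 to 24 weeks, not the Week 24 proportion. That is true. The Kaplan-Meier estimates would carry the endpoint; the test accompanies them.

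**Conclusion.** The point holds as a matter of efficiency and of an unassigned analysis set. After Version 3.0 removed the 24-week minimum, CMH on the Week 24 set is valid but wasteful. It sets aside about 37% to 89% of randomized subjects and leaves about 58% down to 10% power, against 75% to 83% for a censored-data test on all ITT subjects. These figures rest on the plan's hazards, the assumed accrual of 50 subjects over 104 down to 26 weeks, the assumed strata, and a cutoff at the 22nd event.

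The inflated proportions in step 6 of the working are a risk only if full ITT is used with closed-out subjects counted as successes, which Section 7.7.1 points away from. The endpoint lies outside the gatekeeping and Hochberg procedure, so nothing here weakens the primary analysis or the control of type I error. It is a worthwhile, inexpensive improvement.

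**What to change.** In Section 7.7.5.2, remove this endpoint from the CMH list and state:

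- The proportion without confirmed recurrence at Week 24 is the Kaplan-Meier estimate by arm in the full ITT set, with log-log 95% confidence intervals and numbers at risk.
- Arms are compared by the stratified log-rank test with follow-up truncated at Week 24.

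In Section 7.5, state that the ITT Week 24 set does not apply to this endpoint.

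If a test of the Week 24 proportion itself is preferred, a permutation test of the Kaplan-Meier difference had power of 67% to 73% for accrual over 26 to 68 weeks, with type I error of 1.0% to 1.7% at 52 weeks. A plain Greenwood z-test should be avoided: with few at risk its one-sided error reached 4% to 13% under the higher hazards simulated.

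The cost is wording only, with no new data. The approach relies on non-informative administrative censoring, in line with the missing-at-random statement in Section 7.7.1. If accrual is so fast that few subjects reach Week 24, the Kaplan-Meier estimate is unreliable too, which is why numbers at risk must be shown. Coverage of the log-log interval with few at risk was not checked here.
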